10.2.5.5 Laboratory Safety Data

The following clinical laboratory tests will be performed at the study visits outlined in [Table 1](#).

Table 10: Clinical Laboratory Tests to be Performed During Study

Hematology:	Clinical Chemistry:	Urinalysis
Hemoglobin*	Sodium*	Protein
Hematocrit*	Potassium*	Glucose
Mean corpuscular volume (MCV)	Chloride*	Specific gravity
Erythrocyte count (RBC)	Bicarbonate*	Blood
Leukocytes (WBC)*	Glucose (nonfasting)	
Platelets*	Blood urea nitrogen (BUN)*	
Differential:*	Creatinine*	Microscopic examination will be performed if indicated
Neutrophils	Calcium*	
Lymphocytes	Magnesium*	
Monocytes	Phosphate	
Eosinophils	Alkaline phosphatase*	
Basophils	Alanine transaminase (ALT/SGPT)*	
	Aspartate transaminase (AST/SGOT)*	
Differential should be reported consistently throughout the study as either an absolute count (preferred) or as a percentage.	Total protein	
	Albumin	
	Lactate Dehydrogenase (LDH)	
	Total Bilirubin*	
	Uric acid	
	Amylase*	
	Lipase*	
Coagulation Panel		
Prothrombin time (PT)/		
Partial thromboplastin time (PTT)		
International normalized ratio (INR)		
The coagulation panel should be done at screening		

* On study treatment days, tests must be performed within 24 hours prior to dosing, and results must be reviewed prior to study treatment administration. For all other laboratory tests, results from the prior visit must be reviewed before the administration of study treatment. See Section 8.2 for guidance regarding dosing modifications/delays due to toxicity, including laboratory abnormalities.

Investigators must document their review of each laboratory report by signing or initialing and dating each report, as well as addressing the clinical significance and causality (for significant abnormalities). Clinically significant abnormal laboratory results should be repeated as soon as possible (preferably within 24 to 48 hours). Section 10.2.5.1 provides further guidance as to when abnormal laboratory results are to be reported as adverse events.

10.2.5.6 Other Safety Data

The following evaluations will also be performed during the study to measure the safety and tolerability of study treatment:

- ECGs
- Vital sign measurements
- Physical examinations

11 SAFETY MONITORING

As this study is a single-arm, Phase 2 design, an IDMC will not be utilized. To ensure both study integrity and patient safety, processes are in place within Celldex for regular review and monitoring of emerging safety data. Celldex will regularly communicate study conduct and safety information to participating investigators.

12 STATISTICAL CONSIDERATIONS

Detailed methodology for summary and statistical analyses of the data collected in this trial will be documented in a Statistical Analysis Plan (SAP), which will be developed and maintained by Celldex.

The SAP may modify the plans outlined in the protocol; however, any major modifications of the primary endpoint definition and/or its analysis will also be reflected in a protocol amendment.

12.1 Sample Size and Power Calculation

The original sample size for the study was based on Simon's 2-stage MinMax design. The first stage was completed, and the futility stopping rule was not met. The current amendment will increase the total sample size from 30 to approximately 45 treated patients, including at least 15 patients whose tumors harbor a FAT1 mutation based on retrospective gene sequencing.

Table 11 shows confidence intervals associated with a range of observed ORRs in all treated patients (n=45) and in those who are FAT1 mutation-positive (n=15) that would provide sufficient precision to rule out < 10%, < 15%, and < 20% ORR based on the lower 95% confidence bound for different underlying true response rates (true p). The table also shows the likelihood of observing at least the number of responses associated with each of these thresholds (power).

If the true response rate is $\geq 30\%$, a sample size of 45 treated patients provides sufficient power to rule out < 10% ORR; if the true response rate is $\geq 40\%$, then the study is adequately powered to rule out < 20% ORR.

A cohort size of 15 treated patients in the FAT1 mutation-positive cohort provides $\geq 70\%$ power to rule out < 10% ORR if the true response is $\geq 30\%$; $\geq 78\%$ power to rule out < 15% ORR if the true ORR is $\geq 40\%$; and $\geq 70\%$ power to rule out < 20% ORR if the true ORR is $\geq 50\%$.

Table 11: Observed ORR and Associated Precision and Power Calculations under Varying Cohort Sample Sizes and Underlying Response Rates

Cohort	Observed No. Responses	95% CI ^a of ORR	Power: P (No. observed responses $\geq r$ true p)*100			
	r (ORR)	(%)	true p = 50%	true p = 40%	true p = 30%	true p = 20%
All	9/45 (20.0%)	(9.6, 34.6)	> 99%	> 99%	95%	56%
Treated Patients	12/45 (26.7%)	(14.6, 41.9)	> 99%	98%	74%	17%
n=45	15/45 (33.3%)	(20.0, 49.0)	> 99%	86%	37%	2%
FAT1 mutation positive	4/15 (26.7%)	(7.8, 55.1)	98%	91%	70%	35%
n=15	5/15 (33.3%)	(11.8, 61.6)	94%	78%	48%	16%
	7/15 (46.7%)	(21.3, 73.4)	70%	39%	13%	2%

^a Clopper-Pearson

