Overview of Study Design:	This is an open-label, multicenter Phase 2 study of CDX-3379 in combination with cetuximab in patients with cetuximab-resistant HNSCC. The study was initially designed according to a Simon's 2-stage design in which one tumor response (complete response [CR] or partial response [PR]) would need to be observed in the first 13 evaluable patients before completion of accrual to a total of 27 evaluable patients. Patients who discontinue treatment in the absence of progression/symptomatic deterioration/death before the first tumor assessment will be considered unevaluable for primary analysis and will be replaced. Following completion of stage 1 of the study, where 1 complete response was observed, emerging biomarker data were reviewed to assess correlation with efficacy in the overall CDX-3379 development program. In a small patient dataset, FAT1 and NOTCH1, NOTCH2 and NOTCH3 mutations appeared to be associated with clinical activity, including objective response and durable stable disease. Given these findings, the study design has been amended to enroll up to approximately 45 total patients, including at least 15 patients whose tumor harbor a FAT1 mutation based on retrospective

	
gene sequencing. Screening tissue samples will be required to be submitted as directed by the Sponsor at the time of enrollment to allow for gene sequencing and tracking the number of patients whose tumor harbor a FAT1 mutation.
 
Tumor assessments will be performed approximately every 6 weeks during treatment. Patients who discontinue treatment in the absence of progression will continue to have assessments approximately every 12 weeks until documented progression or initiation of alternate anticancer therapies. Tumor response will be assessed by the investigator in accordance with RECIST 1.1 guidelines (Eisenhauer, et al. 2009) (Section 10.2.1 and Appendix 2).
 
Continuous evaluation of toxicity will be performed by the investigators and Celldex throughout the entire course of patient treatment and through 30 days following the last dose of CDX-3379. Subsequently, patients will be followed for survival, with contact every 12 weeks until study closure.

	[REDACTED]

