7 INVESTIGATIONAL PLAN

7.1 Overall Design and Plan of the Study

This is an open-label, multicenter Phase 2 study of CDX-3379 in combination with cetuximab in patients with cetuximab-resistant HNSCC. Patients will be treated with CDX-3379 plus cetuximab until progressive disease, unacceptable toxicity, or other criteria for discontinuation of study treatment (Section 7.4.1) are met.

The study was initially designed according to a Simon's 2-stage design in which one tumor response (CR or PR) would need to be observed in the first 13 evaluable patients before completion of accrual to a total of 27 evaluable patients. Patients who discontinue treatment in the absence of progression/symptomatic deterioration/death before the first tumor assessment will be considered unevaluable for primary analysis and will be replaced. Following completion of stage 1 of the study, where 1 complete response was observed, emerging biomarker data were reviewed to assess correlation with efficacy. In the overall CDX-3379 development program, in a small patient dataset, FAT1 and NOTCH1, NOTCH2 and NOTCH3 mutations appeared to be associated with clinical activity including objective response and durable stable disease. Given these findings, the study design has been amended to enroll up to approximately 45 total patients, including at least 15 patients whose tumor harbor a FAT1 mutation based on retrospective gene sequencing. Screening tissue samples will be required to be submitted as directed by the Sponsor at the time of enrollment to allow for gene sequencing and tracking the number of patients whose tumor harbor a FAT1 mutation.

Tumor assessments will be performed approximately every 6 weeks during treatment. Patients who discontinue treatment in the absence of progression will continue to have assessments approximately every 12 weeks until documented progression or initiation of alternate anticancer therapies. Tumor response will be assessed by the investigator in accordance with RECIST 1.1 guidelines (Eisenhauer, et al. 2009) (Section 10.2.1 and Appendix 2).

Continuous evaluation of toxicity will be performed by the investigators and Celldex throughout the entire course of patient treatment and through 30 days following the last dose of CDX-3379. Subsequently, patients will be followed for survival, with contact every 12 weeks until study closure.

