PR	partial response
PR interval	period from the beginning of the P wave until the beginning of the QRS complex
PT	preferred term
PTEN	phosphatase and tensin homolog
QRS interval	combination of the Q wave, R wave, and S wave
QT interval	period from the beginning of the QRS complex to the end of the T wave
QTc	corrected QT interval
RECIST	Response Evaluation Criteria in Solid Tumors
RR interval	time elapsed between two successive R waves
SAE	serious adverse event
SAP	statistical analysis plan
SCI	Statistics Collaborative, Inc.
SD	stable disease
SOC	system organ class
$t^{1/2}$	apparent elimination half-life
TEAE	treatment emergent adverse event
TdP	torsades de pointes
WHO	World Health Organization

Definitions

Adverse event	An adverse event (AE) is any reaction, side effect, or other untoward event, regardless of relationship to study drug, which occurs anytime during the study in a patient administered study treatment.
All treated population	All patients treated with CDX-3379
Response-evaluable population	All patients who have measurable disease at baseline and receive one full dose of both CDX-3379 and cetuximab and have post-baseline tumor response assessment or discontinue study prematurely for disease progression, symptomatic deterioration, or death.
Serious AE	An AE occurring at any dose that: results in death; is a life-threatening experience; requires inpatient hospitalization or prolongation of an existing hospitalization; results in a persistent or significant disability/incapacity; or is a congenital anomaly/birth defect in the offspring of a patient who received study drug.
Treatment-emergent AE	AEs with an onset time after the initial dose of study drug.

1. Introduction

This statistical analysis plan (SAP) is based on Celldex's Protocol CDX3379-04 Amendment 1 [A Phase 2, Multicenter, Open-label Study to Evaluate the Efficacy and Safety of CDX-3379 in Combination with Cetuximab in Patients with Advanced Head and Neck Squamous Cell Carcinoma], dated June 28, 2019. The SAP summarizes key aspects of the study to provide context for statistical methods and presents details of the planned statistical methods addressing the study aims. To the extent that analyses described in this SAP differ from those described in the protocol, the methods of the SAP prevail. Any deviations to the SAP will be documented in the final clinical study report. Pharmacokinetic (PK) data analyses will be addressed in a separate analysis plan.

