2.1. Study design

This is an open-label, multicenter Phase 2 study of CDX-3379 in combination with cetuximab in patients with cetuximab-resistant head and neck squamous cell carcinoma (HNSCC). In this single-arm study, patients will be treated with CDX-3379 plus cetuximab until progressive disease, unacceptable toxicity, or other criteria for discontinuation of study treatment are met.

Prior to Amendment 1 of the protocol, the study was initially designed according to a Simon's 2-stage design in which one tumor response (complete response [CR] or partial response [PR]) would need to be observed in the first 13 evaluable patients before completion of accrual to a total of 27 evaluable patients. Patients who discontinue treatment in the absence of progression/symptomatic deterioration/death before the first tumor assessment will be considered unevaluable for primary analysis and will be replaced. Following completion of stage 1 of the study, where one CR was observed, emerging biomarker data were reviewed to

assess correlation with efficacy. In the overall CDX-3379 development program, in a small patient dataset, FAT Atypical Cadherin 1 (FAT1) and NOTCH1, NOTCH2 and NOTCH3 mutations appeared to be associated with clinical activity including objective response and durable stable disease.

Given these findings, the study design was amended to enroll up to approximately 45 total patients, including at least 15 patients whose tumors harbor a FAT1 mutation based on retrospective gene sequencing. Screening tissue samples will be required to be submitted as directed by Celldex at the time of enrollment to allow for gene sequencing and tracking the number of patients whose tumors harbor a FAT1 mutation.

Tumor assessments will be performed approximately every six weeks during treatment. Patients who discontinue treatment in the absence of progression will continue to have assessments approximately every 12 weeks until documented progression or initiation of alternate anticancer therapies. The investigator will assess tumor response in accordance with Response Evaluation Criteria in Solid Tumors (RECIST) 1.1 guidelines [2] (see Section 10.3).

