4.9. Sample size determination and power calculation

The original sample size for the study was based on Simon's 2-stage MinMax design. The first stage was completed, and the futility stopping rule was not met. Protocol Amendment 1 increased the total sample size from 30 to approximately 45 treated patients, including at least 15 patients whose tumors harbor a FAT1 mutation based on retrospective gene sequencing.

According to the protocol, the planned sample size of 45 treated patients provides >80% power to rule out <20% ORR based on the lower 95% confidence bound for the for different underlying true response rates if the true response rate is $\geq 40\%$.

The cohort size of 15 treated patients in the FAT1 mutation-positive cohort provides nearly 80% power to rule out <15% ORR if the true response rate is $\geq 40\%$.

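### The power quoted for n=45 is unconditional; given plausible Stage 1 results, power to rule out an ORR below 20% at a true 40% was about 28-54%, not 86%

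*Protocol*

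**What the plan says.** Protocol 12.1 explains that the original size came from a Simon two-stage design, that "The first stage was completed, and the futility stopping rule was not met", and that the amendment raises the total from 30 to about 45 treated patients. It then makes two claims for the whole cohort. At a true rate of at least 30%, "a sample size of 45 treated patients provides sufficient power to rule out < 10% ORR"; at a true rate of at least 40%, "then the study is adequately powered to rule out < 20% ORR". The synopsis makes the same claims. SAP 4.9, attributing the figure to the protocol, says that "the planned sample size of 45 treated patients provides >80% power to rule out <20% ORR" at a true rate of at least 40%.

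Table 11 defines power as the probability of at least r responses given the true rate p. For n=45 it lists r = 9, 12 and 15, against thresholds of 10%, 15% and 20%. The 15/45 entry at a true rate of 40% is 86%.

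On Stage 1, the synopsis says that one response "would need to be observed in the first 13 evaluable patients before completion of accrual to a total of 27 evaluable patients". Protocol 7.1 reports: "Following completion of stage 1 of the study, where 1 complete response was observed, emerging biomarker data were reviewed to assess correlation with efficacy". SAP 2.1 agrees: "Following completion of stage 1 of the study, where one CR was observed". The 45 is a total, and Protocol 12.4 runs the primary efficacy analysis in all patients treated with CDX-3379, so Stage 1 patients are included.

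**The concern.** Power is the stated reason for n=45. When that number was chosen, part of the 45 had already been observed, with one complete response reported from a stage designed for 13 evaluable patients. A probability that treats all 45 outcomes as still open does not describe what the enlarged study could be expected to show. A committee weighing the increase from 30 to 45 would read 86%, or more than 80%, as the chance that the amended study excludes an ORR below 20% if the drug works at 40%. No passage in the text reviewed gives the chance that remained.

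**Working it through.** **Inputs.** Total n = 45, all treated (Protocol 7.1, 12.1, 12.4). Two-sided 95% Clopper-Pearson interval (Protocol 12.5.1, SAP 6.1). True rate 40% for the 20% threshold (Protocol 12.1). Stage 1: 13 evaluable planned and 1 complete response reported (Protocol 7.1). The number treated in Stage 1 (n1) and the total responders (x1) are assumptions. Protocol 7.4 replaces unevaluable patients, so n1 may exceed 13, and partial responses are not mentioned, so x1 may exceed 1.

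**Step 1: reproduce the plan's figure.** The lower bound is 20.00% for 15/45 and 18.17% for 14/45, so 15 is the correct cut-off. P(Bin(45, 0.40) ≥ 15) = 85.7%, which matches 86%.

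**Step 2: condition on Stage 1.** The power that remains is P(Bin(45 − n1, p) ≥ 15 − x1), where p is the rate in the remaining patients. For n1 = 13 and x1 = 1, at least 14 of the remaining 32 (43.8%) must respond: P(Bin(32, 0.40) ≥ 14) = 39.6%. Other counts, all at p = 40%:

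| Stage 1 (responders/treated) | Needed from remaining patients | Power |
|---|---|---|
| 1/13 | 14 of 32 | 39.6% |
| 1/14 | 14 of 31 | 34.0% |
| 1/15 | 14 of 30 | 28.5% |
| 2/13 | 13 of 32 | 53.8% |
| 3/13 | 12 of 32 | 67.7% |
| 4/13 | 11 of 32 | 79.5% |
| 5/13 | 10 of 32 | 88.4% |

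The first four rows are the plausible cases and give the range of about 28-54%. The last three show how many unreported responders it would take to restore 80%.

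**Step 3: rate needed for 80%.** Solving P(Bin(32, p) ≥ 14) = 0.80 gives p of about 50%; at exactly 50% the power is 81.1%.

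**Step 4: what drives the drop.** Conditioning only on having passed futility (at least 1 response in 13) gives 85.8%, so continuation itself costs nothing. The loss comes from the low observed count.

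**Step 5: the 10% and 15% rows for n=45.** This check does not depend on Stage 1. Protocol 12.1 says a threshold is ruled out by the lower 95% confidence bound.

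| Threshold | Table 11 count (lower bound) | Smallest qualifying count (lower bound) | Unconditional power: Table 11 → qualifying |
|---|---|---|---|
| 10%, true 30% | 9/45 (9.6%) | 10/45 (11.2%) | 95% → 90.7% |
| 15%, true 40% | 12/45 (14.6%) | 13/45 (16.4%) | 98% → 95.5% |

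With the qualifying count of 10 and an assumed 1/13 in Stage 1, the 10% statement at a true 30% has conditional power P(Bin(32, 0.30) ≥ 9) = 65.6%.

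**The case against.** A reader might infer that the 86% is a calculation error. It is not. Table 11's header conditions on the true rate only, and the figure is right for that quantity. Nor is Stage 1 concealed: both documents report its completion and the complete response. What is missing is one derived number.

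A reader might also take 39.6% as the established power of the study. The documents do not support that either. It needs exactly 13 treated and exactly one response. Appendix 4 says that Stage 1 data were added to Sections 5.3.2 and 5.4, which are not in the text reviewed, so the true counts may be stated there. It also needs a 40% rate in the remaining patients, which sits poorly with 1/13: at a true 40%, one or fewer responses in 13 has probability 1.3%, and the exact 95% interval for 1/13 is 0.2-36.0%. Later patients may differ, since Appendix 4 records that HPV-negative tumors are now required and the amendment asks for at least 15 FAT1-positive patients. A single rate for all 45 may therefore not apply. This is why the conditional figure has to be stated for the remaining patients. It does not rescue the 86%, which itself assumes 40% in all 45.

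The strongest objection is that the study is one of estimation. Protocol 12.3 says no formal hypothesis testing is planned, and no decision rule in the plan uses 15/45. That stands, and it limits the consequence to the sample-size justification. Both documents nevertheless chose power as that justification. SAP 4.9 only reports the protocol's number, but does so without saying what the number conditions on.

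**Conclusion.** The point holds as one about how the justification for n=45 is stated. The 86% is a correct unconditional probability. If the remaining patients respond at 40%, the power left at Amendment 1 to rule out an ORR below 20% was about 28-54% over the four plausible cases, and below 80% unless Stage 1 had at least 5 responders in 13. The exact value depends on Stage 1 counts not visible in the text reviewed. It would not be right to conclude that the sample size is invalid or that the final ORR and its interval are compromised: neither depends on this probability. The 9/45 and 12/45 entries are a separate, smaller inconsistency with the protocol's own lower-bound rule, worth about 2 to 5 percentage points of unconditional power at the rates shown.

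**What to change.** 1. Keep Table 11 in Protocol 12.1 and the synopsis, but label its power columns as unconditional, that is, before any outcomes are known.
2. Beside the two power statements for n=45, report conditional power, P(at least r − x1 responses in the 45 − n1 remaining patients), from the actual Stage 1 treated and responder counts. Give the true ORR in the remaining patients at which it reaches 80% (about 50% for the 20% threshold if Stage 1 was 1/13).
3. In SAP 4.9, mark the figure of more than 80% as unconditional.
4. Separately, for n=45 use 10/45 for the 10% threshold (90.7% at a true 30%) and 13/45 for the 15% threshold (95.5% at a true 40%).

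The cost is a text change in three places and two revised table rows. The stated power becomes less favourable. The sample size, the primary analysis and the confidence interval stay as they are.

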Statistical Methods:	
Sample Size
 
The original sample size for the study was based on Simon's 2-stage MinMax design. The first stage was completed, and the futility stopping rule was not met. The current amendment will increase the total sample size from 30 to approximately 45 treated patients, including at least 15 patients whose tumors harbor a FAT1 mutation based on retrospective gene sequencing.
 
Shown below are the confidence intervals associated with a range of observed ORRs in all treated patients (n=45) and in those who are FAT1 mutation-positive (n=15) that would provide sufficient precision to rule out < 10%, < 15%, and < 20% ORR based on the lower 95% confidence bound for different underlying true response rates (true p). The table also shows the likelihood of observing at least the number of responses associated with each of these thresholds (power).
 
If the true response rate is $\geq 30\%$, a sample size of 45 treated patients provides sufficient power to rule out < 10% ORR; if the true response rate is $\geq 40\%$, then the study is adequately powered to rule out < 20% ORR.
 
A cohort size of 15 treated patients in the FAT1 mutation-positive cohort provides $\geq 70\%$ power to rule out <10% ORR if the true response is $\geq 30\%$; $\geq 78\%$ power to rule out <15% ORR if the true ORR is $\geq 40\%$; and $\geq 70\%$ power to rule out <20% ORR if the true ORR is $\geq 50\%$.
 
Observed ORR and Associated Precision and Power Calculations Under Varying Cohort Sample Sizes and Underlying Response Rates
 
  
 Cohort	Observed No. Responses r (ORR)	95% CI ^a of ORR (%)	Power: P (No. observed responses $\geq r$ true p)*100	
 
 true p = 50%	true p = 40%	true p = 30%	true p = 20%	
   
 All Treated Patients n=45	9/45 (20.0%) 12/45 (26.7%) 15/45 (33.3%)	(9.6, 34.6) (14.6, 41.9) (20.0, 49.0)	> 99% > 99% > 99%	> 99% 98% 86%	95% 74% 37%	56% 17% 2%	
 
 FAT1 mutation positive n=15	4/15 (26.7%) 5/15 (33.3%) 7/15 (46.7%)	(7.8, 55.1) (11.8, 61.6) (21.3, 73.4)	98% 94% 70%	91% 78% 39%	70% 48% 13%	35% 16% 2%	
  
 
^a Clopper-Pearson
 
Analysis Population(s)
 
All treated population: All patients treated with CDX-3379. The primary efficacy analysis as well as all safety, PK, and biomarker analyses will be performed in this population. Efficacy analyses will also be conducted in the following subgroups: FAT1 mutation-positive treated patients, FAT1 or NOTCH mutation-positive treated patients, and all treated patients with a primary tumor site of oral cavity.
	Cohort	Observed No. Responses r (ORR)	95% CI ^a of ORR (%)	Power: P (No. observed responses $\geq r$ true p)*100				true p = 50%	true p = 40%	true p = 30%	true p = 20%	All Treated Patients n=45	9/45 (20.0%) 12/45 (26.7%) 15/45 (33.3%)	(9.6, 34.6) (14.6, 41.9) (20.0, 49.0)	> 99% > 99% > 99%	> 99% 98% 86%	95% 74% 37%	56% 17% 2%	FAT1 mutation positive n=15	4/15 (26.7%) 5/15 (33.3%) 7/15 (46.7%)	(7.8, 55.1) (11.8, 61.6) (21.3, 73.4)	98% 94% 70%	91% 78% 39%	70% 48% 13%	35% 16% 2%

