6.1. Primary efficacy endpoint

The primary efficacy endpoint of this study is ORR, defined as the percentage of patients who achieve a best response of CR or PR, confirmed according to RECIST 1.1. That is, the criteria for response (CR or PR) must be met again at the next scheduled tumor assessment no sooner than 28 days after the initial documentation. Best response is recorded between the date of first dose and the date of documented progression per RECIST 1.1 or the date of subsequent anti-cancer treatment, whichever occurs first. Anti-cancer treatment includes (a) systemic anti-cancer therapy or (b) radiation or surgical resection of a target or non-target lesion. All anti-cancer treatments will be reviewed and confirmed by the Celldex medical team. For patients without documented progression or subsequent anti-cancer treatment, all available tumor assessments will contribute to the best response assessment.

The number and percentage of patients in each category of BOR (CR, PR, SD, PD, or not evaluable [NE]) will be summarized for the all treated population. ORR will be calculated as defined above, and the corresponding two-sided 95% exact CI will be calculated using the Clopper-Pearson method.

A waterfall plot showing the maximum change from the baseline sum of the diameters of target lesions will be produced for the response-evaluable population. Subgroup waterfall plots may be produced.

A swimmer plot will be produced to present individual patient's tumor response and duration of response over time.

A spider plot will be produced to present change in an individual patient's tumor size with tumor size relative to baseline plotted against month from baseline scan; new lesion and end of treatment dates will be annotated in the plot. Subgroup spider plots may be produced.

Change from baseline in tumor size will be calculated as: Sum of diameters at Week X (mm) – Sum of diameters at Baseline (mm). Percent change from baseline in tumor size will be calculated as: (Sum of diameters at Week X (mm) – Sum of diameters at Baseline (mm)) / Sum of diameters at Baseline (mm) * 100%.

All primary and secondary efficacy outcomes (BOR, DOR if applicable, date of PD if applicable, PFS status, and OS status) will be presented in a single by-patient listing. Individual timepoint assessment data for each lesion will be presented in a separate listing.

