6.3. Subgroup analyses

The primary and secondary efficacy analyses will be repeated for each of the following subgroups using the methods described in Sections 6.1 and 6.2:

- FAT1 mutation status (positive vs. negative) among treated subjects who have evaluable FAT1 results
- FAT1/NOTCH mutation status (positive for either FAT1 or NOTCH vs. negative for both) among treated subjects who have evaluable FAT1 and NOTCH results
- Primary tumor site (oral cavity vs. other) in all treated subjects

Specifically, the number and percentage of patients in each category of BOR will be summarized for each subgroup. The estimates of ORR, CBR, and DCR and the corresponding two-sided 95% exact CIs for each subgroup will be presented in forest plots for each endpoint.

DOR, PFS, and OS will be estimated in each subgroup using the KM product limit method and displayed graphically with the estimated median and two-sided 95% CI. The median estimates for each subgroup will also be presented in forest plots.

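### FAT1 cohort power is overstated: 4/15 and 5/15 do not exclude 10% and 15% under the planned Clopper-Pearson interval, so power is about 48% and 60%, not 70% and 78%

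*Protocol*

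**What the plan says.** Protocol 12.1 presents Table 11 as a set of response counts precise enough to "rule out < 10%, < 15%, and < 20% ORR based on the lower 95% confidence bound". It defines power as "the likelihood of observing at least the number of responses associated with each of these thresholds (power"). The table footnote names Clopper-Pearson as the interval method.

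For 15 patients the section makes three claims, the first being that the "FAT1 mutation-positive cohort provides $\geq 70\%$ power to rule out < 10% ORR if the true response is $\geq 30"%. The second is at least 78% power to exclude 15% at a true rate of 40%. The third is at least 70% power to exclude 20% at a true rate of 50%. The Protocol synopsis repeats the table and all three claims. SAP 4.9 keeps only the second, saying the cohort "provides nearly 80% power to rule out <15% ORR if the true response rate is" at least 40%.

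The analysis method agrees with the footnote. For the primary endpoint, SAP 6.1 states that "the corresponding two-sided 95% exact CI will be calculated using the Clopper-Pearson method". SAP 6.3 applies the same methods to the FAT1 subgroup, where "the corresponding two-sided 95% exact CIs for each subgroup will be presented in forest plots".

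**The concern.** Each power figure is meaningful only if the count it refers to meets the criterion. Four of the six rows of Table 11 fail it on their own printed limits: 4/15 (7.8% against 10%), 5/15 (11.8% against 15%), 9/45 (9.6% against 10%) and 12/45 (14.6% against 15%). Only 7/15 (21.3%) and 15/45 (20.0%) clear their thresholds.

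The FAT1 rows matter most. The FAT1 and NOTCH findings prompted the amendment, and these figures are the plan's only quantitative support for a cohort of 15. A reader would expect 4/15 to exclude 10%, with a 70% chance of reaching that count if the true rate is 30%. The interval that will be reported for 4/15 includes 10%.

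**Working it through.** **Inputs.** n = 15 and 45; thresholds 10%, 15% and 20%; true rates from Table 11; two-sided 95% Clopper-Pearson (Table 11 footnote, SAP 6.1 and 6.3).

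**Formulas.**
- Lower limit for r responses in n: the 0.025 quantile of a Beta(r, n − r + 1) distribution.
- Power: P(X ≥ r | n, p), the exact binomial upper tail, where r is the smallest count whose lower limit reaches the threshold.

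**Step 1. Reproduce the printed figures.** The tails at the tabled counts are P(X ≥ 4 | 15, 0.3) = 70.3%, P(X ≥ 5 | 15, 0.4) = 78.3% and P(X ≥ 7 | 15, 0.5) = 69.6%. These match the printed 70%, 78% and 70%. The printed intervals also reproduce as two-sided Clopper-Pearson. The tails and the intervals are each correct; the link from count to threshold is not.

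**Step 2. Find the counts that meet the criterion, n = 15.**

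| r | Lower limit | Excludes 10% | Excludes 15% | Excludes 20% |
|---|---|---|---|---|
| 4 | 7.79% | no | no | no |
| 5 | 11.82% | yes | no | no |
| 6 | 16.34% | yes | yes | no |
| 7 | 21.27% | yes | yes | yes |

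The counts needed are 5, 6 and 7. Table 11 uses 4, 5 and 7.

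**Step 3. Power at those counts.** Remove the one count that does not qualify from each tail:
- Exclude 10%, p = 30%: P(X = 4) = 1365 × 0.3⁴ × 0.7¹¹ = 0.2186, so P(X ≥ 5) = 0.7031 − 0.2186 = 0.4845, or 48.5%. Table 11 already prints 48% for 5/15 at a true rate of 30%.
- Exclude 15%, p = 40%: P(X = 5) = 3003 × 0.4⁵ × 0.6¹⁰ = 0.1859, so P(X ≥ 6) = 0.7827 − 0.1859 = 0.5968, or 59.7%.
- Exclude 20%, p = 50%: 69.6%, unchanged.

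The overstatements are 70.3 − 48.5 = 21.8 points and 78.3 − 59.7 = 18.6 points.

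**Step 4. The same check for n = 45.**

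| Threshold | Tabled count (lower limit) | Count needed (lower limit) | Tabled power | Corrected power |
|---|---|---|---|---|
| 10% | 9 (9.58%) | 10 (11.20%) | 95% at p = 30% | 90.7% |
| 15% | 12 (14.60%) | 13 (16.37%) | 74% at p = 30%; 98% at p = 40% | 62.0%; 95.5% |
| 20% | 15 (20.001%) | 15 | 86% at p = 40% | 85.7% |

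**Step 5. Could another reading of the bound rescue the FAT1 rows?** Lower limits for 4/15 and 5/15 under other methods:
- one-sided 95% Clopper-Pearson: 9.67% and 14.17%
- mid-P: 9.1% and 13.4%
- Jeffreys: 9.7% and 14.0%
- Wald: 4.3% and 9.5%
- Wilson: 10.9% and 15.2%

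Only Wilson clears both thresholds, and neither document names it.

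**The case against.** **A one-sided bound may have been meant.** Protocol 12.1 does not state the sidedness of the lower 95% bound. With a one-sided 95% Clopper-Pearson bound, 9, 12 and 15 are exactly the smallest qualifying counts of 45 (limits 10.85%, 16.17% and 21.80%). This is a fair defence of the 45-patient rows, although the table prints two-sided intervals and the SAP specifies two-sided intervals. It does not help 4/15 or 5/15 (Step 5).

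**A different interval may have set the counts.** A two-sided Wilson criterion reproduces all six tabled counts, so the counts may have come from one method and the intervals from another. That is inference, and the analysis will use Clopper-Pearson.

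**Fifteen is a minimum.** True, but the power is claimed for a cohort of exactly 15. Under Clopper-Pearson, the first size with at least 70% power for 10% against 30% is 23 (73.1%). The first with at least 78% for 15% against 40% is 24 (80.8%). A few extra patients would not restore the claims.

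**The consequences are limited.** This objection stands. The aim is estimation, Protocol 12.3 plans no formal hypothesis test, SAP Section 6 calls the FAT1 analyses supportive, and no visible decision rule uses 4/15 or 5/15. Each subgroup result will carry its own exact interval, so the reported estimates are unaffected. Table 11 also shows the failing limits beside the counts. SAP 4.9, however, repeats the nearly 80% figure without the table.

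**Conclusion.** The concern holds. With 15 FAT1-positive patients and the planned two-sided 95% Clopper-Pearson interval, power to exclude 10% at a true rate of 30% is 48.5%, against at least 70% stated. Power to exclude 15% at a true rate of 40% is 59.7%, against at least 78% in the Protocol and nearly 80% in the SAP. These two results do not depend on whether the Clopper-Pearson bound is read as one-sided or two-sided.

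The corrections to 9/45 and 12/45 do rest on the two-sided reading, which is the one the table and SAP use. The text conclusions for 45 patients stand either way: at least 90.7% for 10% at a true 30%, and 85.7% for 20% at a true 40%, consistent with the SAP's statement of more than 80%. The third FAT1 claim is sound apart from rounding (69.6%).

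The error lies in the stated justification of the FAT1 cohort. It does not alter the analysis, but the figures must be corrected because the design does not deliver them.

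**What to change.** Amend the Protocol synopsis, Protocol 12.1 with Table 11, and SAP 4.9:

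- Replace the tabled counts with 10, 13 and 15 of 45 and 5, 6 and 7 of 15, and recompute the intervals and power columns for the changed rows.
- Restate FAT1 power as about 48% (exclude 10%, true 30%), about 60% (exclude 15%, true 40%) and about 70% (exclude 20%, true 50%). In SAP 4.9, replace the nearly 80% figure with about 60%.
- Restate the 45-patient figure for excluding 10% at a true 30% as about 91%.
- State that the lower bound is that of the two-sided 95% interval.

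The alternative is to name one other interval and use it for both design and analysis. That would change the planned primary analysis, so correcting the table is simpler.

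The cost is wording and one table. Sample size, conduct and analysis stay as they are, but the stated FAT1 power becomes less favourable.
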